 ‡ Multiple publications with overlapping data. Data from the first report were used because patient-level data was provided, allowing calculation of SD, median, and IQR for per-patient total lesion volume.
 ** Average and weighted average Standard Deviations calculated using SD per unit method

Table 5. Reported Total Lesion Volume (Per-Subject) on Post-TAVI DW-MRI - Excluding Subjects Who Experienced a Stroke

Study	N	Per Patient Lesion Volume (cm ³)				
		Range (min, max)	Mean	SD**	Median	IQR [25-75]
Astarci 2013^{37†*}	44	--	1.65	--	--	--
Fairbairn 2012^{38‡}	29	--	1.1	1.1	--	--
Ghanem 2010^{43‡}	21	0, 7.8	1.16	2.08	0.30	0-1.00
Uddin 2013⁴²	45	--	1.74	2.8	--	--
Average	35	--	1.41	2.07	--	--
Weighted Average	--	--	1.49	2.18	--	--

† Multiple publications with overlapping data. Data from the most recent (and largest) report is provided.
* Data from studies reporting separate results from multiple study arms were pooled.
‡ Multiple publications with overlapping data. Data from the first report were used because patient-level data was provided, allowing calculation of SD, median, and IQR for per-patient total lesion volume.
** Average and weighted average Standard Deviations calculated using SD per unit method
‡ Strokes excluded where possible (1 subject with a major stroke [Ghanem 2010] and 2 subjects with unspecified stroke [Fairbairn 2012])

The clinical significance of asymptomatic DW-MRI lesions is incompletely characterized. However, in population-based studies the presence of clinically silent brain infarcts has been associated with frailty, declines in physical function, reduced cognitive ability, depressive symptoms, and an increased risk of subsequent stroke or TIA.^{32, 45, 46} Several studies have found an association between DW-MRI lesions and neuropsychological deficits after conventional valve surgery,^{47, 48} and DW-MRI lesions have also been associated with chemical markers of neuronal damage that in turn correlate with postoperative cognitive deficits and embolic stroke.⁴⁹

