12.3 Analysis Populations

12.3.1 Efficacy Intention to Treat (eITT) Analysis Population

The efficacy Intention to Treat (eITT) analysis population is defined as:

- Subjects who are enrolled in the trial and randomized to a treatment group, regardless of treatment actually received AND
- Who do not have conversion to surgery or prolonged cardiac arrest (>3 minutes) prior to the post-procedure DW-MRI

The eITT population of evaluable (i.e., not Roll-In) subjects will be used for the primary analysis of the primary efficacy endpoint, the primary analysis of the secondary hypothesis-driven endpoints, and the primary analysis of all secondary neurologic efficacy endpoints.

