- If both had a stroke on same day, the comparison moves on to the next tier.
- Assuming neither experiences a stroke or death before 30 days, if Subject A experiences NIHSS worsening, and Subject B does not experience NIHSS worsening, Subject A loses (score -1) and Subject B wins (score +1). In case both have NIHSS worsening the patient with the lesser worsening wins.
- Assuming neither subject experiences a stroke or death before 30 days or NIHSS worsening from baseline, if Subject A has no cerebral ischemic lesions on DW-MRI and Subject B has a cerebral ischemic lesion on DW-MRI, Subject A wins (score +1) and Subject B loses (Score -1).
- Assuming neither subject experiences a stroke or death before 30 days, NIHSS worsening from baseline or freedom from DW-MRI cerebral ischemic lesions, if Subject A has a total cerebral ischemic lesion volume of 50 mm³ and Subject B has a total cerebral ischemic lesion volume of 100 mm³, Subject A wins (score +1) and Subject B loses (Score -1).

An illustration of this algorithm is provided in Figure 4 below.

Figure 4. Algorithm of assigning scores by the Finkelstein and Schoenfeld method (*Note: each patient from the intervention group is compared with each and every patient from the control group*)

After all between-subject comparisons have been performed, scores are summed to obtain a cumulative score for each subject, and outcomes between treatment groups are then compared by chi-square test.

This analytic approach does not result in a natural point-estimate (e.g., proportion, mean, median, time-to-event); however, Pocock et al. provided a computational framework for the test statistic called "win ratio". In brief, it is calculated as a proportion of "wins" for each group out of the total number of the pairwise comparisons.

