No imputation of missing DW-MRI data will be performed for the primary analysis. However, in order to assess the sensitivity of results to missing DW-MRI data, multiple imputations with the linear regression approach will be used as the secondary sensitivity analysis. This assessment is necessary because the rate of permanent pacemaker implantation (causing loss to DW-MRI follow-up) may vary according to patient clinical characteristics and prosthesis type.¹⁰⁶ Specifically, missing total volume of cerebral ischemic lesions on post-procedure diffusion-weighted MRI will be imputed via multiple imputation linear regression (10 imputed data sets will be created). The covariates used for the imputation model will be treatment group, age at time of enrollment, body mass index, race, smoking status, creatinine level, hyperlipidemia, hypertension, aortic arch disease burden, porcelain aorta, aortic valve area at baseline, procedure time, country, valve type, balloon post dilatation, arch type, and level of calcification. This creation of the 10 datasets will be carried out using PROC MI in SAS. For each data set, the above-mentioned chi-square test will be carried out on the primary endpoint and one overall chi-square result will be generated from the 10 datasets. For each patient with missing TLV, the crux of multiple imputation is to estimate TLV from patients with non-missing TLV who have similar baseline characteristics as the patient with missing TLV. Thus, in essence, TLV for high risk patients with missing TLV due to pacemaker will theoretically be estimated from patients with similar high risk profiles who do not have pacemakers.

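### The sensitivity imputation of missing lesion volume omits stroke and NIHSS worsening, so part of any stroke difference is scored again in the MRI tiers; the effect is small and cheaply removed

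*Combined protocol and SAP*

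**What the plan says.** Section 12.4.3 confines the imputation to a sensitivity analysis: "No imputation of missing DW-MRI data will be performed for the primary analysis". In that sensitivity analysis, missing total lesion volume is imputed ten times by linear regression in PROC MI, with no transformation stated. The covariate list begins "The covariates used for the imputation model will be treatment group, age at time of enrollment, body mass index, race, smoking status" and ends "aortic valve area at baseline, procedure time, country, valve type, balloon post dilatation, arch type, and level of calcification". It has 17 entries. Treatment group is one of them; stroke, death and NIHSS worsening are not.

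The stated aim is to "estimate TLV from patients with non-missing TLV who have similar baseline characteristics as the patient with missing TLV". Nothing restricts those donors to stroke-free subjects. The efficacy ITT population (12.3.1) does not do so either, since its only clinical exclusion is of subjects who fail this condition: "Who do not have conversion to surgery or prolonged cardiac arrest (>3 minutes) prior to the post-procedure DW-MRI".

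The worked examples in 12.4.3 introduce the lesion-free tier with the condition "Assuming neither subject experiences a stroke or death before 30 days or NIHSS worsening from baseline", and the volume tier has an equivalent condition. Apart from minor exceptions, such as two strokes on the same day, an imputed volume is used only when both members of a pair are free of Tier 1 and Tier 2 events.

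**The concern.** The endpoint conditions on being free of stroke and NIHSS worsening before it looks at the MRI, while the imputation model averages over both. Stroke subjects who were scanned contribute very large volumes to the regression. If one arm has more strokes, its treatment coefficient rises, and its stroke-free subjects with no scan receive volumes that are too large. A difference already credited in Tier 1 is then partly credited again in Tiers 3 and 4. At stake is how cleanly the sensitivity analysis answers its own question, which is whether missing scans alter the result.

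**Working it through.** **1. The plan's own figures (section 4.1.3).** Table 4 includes strokes. Table 5 is the version headed "Excluding Subjects Who Experienced a Stroke". N-weighted means:

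- Table 4: (44×1.65 + 31×2.05 + 22×4.3 + 45×1.74)/142 = 309.05/142 = 2.18 cm³, as printed.
- Table 5: (44×1.65 + 29×1.1 + 21×1.16 + 45×1.74)/139 = 207.16/139 = 1.49 cm³, as printed.

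**2. Implied volume per stroke subject** (difference in totals divided by strokes removed):

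- 22-patient series, one major stroke: 22×4.3 − 21×1.16 = 70.2 cm³. That series' maximum falls from 70.3 to 7.8 cm³ when the stroke is removed.
- 31-patient series, two unspecified strokes: (31×2.05 − 29×1.1)/2 = 15.8 cm³.
- Pooled: (309.05 − 207.16)/3 = 34.0 cm³.

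**3. Expected shift in the treatment coefficient.** With treatment in the model and stroke out, the shift is roughly (control minus device stroke rate) × (stroke volume − 1.49 cm³) × (share of strokes before the scan). Section 4.1.2.1 puts more than half of strokes within two days of the procedure, so shares of 0.5 and 1 are shown.

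| Stroke rates, device v control | Source | Half before scan | All before scan |
|---|---|---|---|
| 5.09% v 7.25% | Table 11a weighted means | 155 to 742 mm³ | 309 to 1484 mm³ |
| 6% v 11% (includes deaths, so an upper case) | 12.2.4.1.2 | 358 to 1718 mm³ | 716 to 3436 mm³ |

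For example, 0.0216 × (15.8 − 1.49) × 0.5 = 0.155 cm³. Each range runs from the 15.8 to the 70.2 cm³ stroke volume. All entries exceed the 50 mm³ absolute difference that 12.2.4.1.2 treats as a win.

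**4. Does the shift appear in imputed values?** Simulation: 150 v 75 subjects, 15% missing at random, no device effect on stroke-free volume, and the upper-case rates of 6% v 11% with all strokes before the scan. Assumptions from outside the documents: lognormal stroke-free volumes (mean about 954 mm³, median about 234 mm³), negative imputed values set to zero. False control-minus-device difference in imputed volume among stroke-free subjects:

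| Stroke volume | Model as written | Stroke added (simulation SE) |
|---|---|---|
| 15.8 cm³ | 612 mm³ | 72 (50) mm³ |
| 34 cm³ | 1494 mm³ | 89 (78) mm³ |
| 70.2 cm³ | 3093 mm³ | 63 (151) mm³ |

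The false net win for the device over all stroke-free pairs was 0.009 to 0.019 on the raw scale and 0.012 to 0.018 on the cube-root scale. With stroke added it lay between −0.004 and 0.002. Since 0.89 × 0.94 = 0.837 of pairs are free of Tier 1 events, the raw-scale figure is about 0.007 to 0.016 of all pairs. Transforming the volume therefore does not cure the leak.

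**5. Effect on net benefit at more moderate inputs** (15% missing, no device effect on volume):

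- Stroke 5.09% v 7.25%, half before the scan: about 0 to 0.005.
- Stroke 5% v 9%, all before the scan: 0.006 to 0.012.
- Adding stroke brings both to about zero.

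The standard error of net benefit is about 0.08, so the largest shift is 0.012/0.08 = 0.15 of a standard error.

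**6. With the plan's lesion-free rates** (27% device v 11% control, 12.2.4.1.2). True net benefit is then about 0.17 to 0.18. The imputation as written errs against the device by 0.017 to 0.022 on the raw scale and by 0.003 to 0.006 on the cube-root scale, because a linear model smooths away the lesion-free zeros. Omitting stroke and NIHSS worsening changes the result by only −0.004 to +0.006.

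**The case against.** The strongest reply is that this touches no decision. The primary analysis does not impute, and the shift is a small fraction of a standard error. That stands, and it is why the point ranks as a cheap improvement and no more.

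Second, the volume contrast is thin. It rests on three patients, one of them with a major stroke, while Tier 1 also counts non-disabling strokes. The other two series have identical rows in Tables 4 and 5. This stands as a limit on the size. It does not remove the mechanism, and because strokes were excluded only where the sources allowed it, the contrast could also be understated.

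Third, one might object to imputing from post-randomisation variables. The plan's list already contains procedure time and balloon post-dilatation, and stroke and NIHSS worsening are parts of the endpoint being analysed, so this does not stand.

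Fourth, section 12.1 defers some detail to the SAP. However, 12.4.3 gives a specific covariate list, and nothing in the documents adds either outcome to it.

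**Conclusion.** The omission is real and its effect is small. With no device effect on volume and 15% missing MRI, it moves net benefit toward the arm with fewer strokes by about 0 to 0.005 at the protocol's weighted stroke rates with half of strokes before the scan, and by up to about 0.012 at 5% v 9% with all before it. The latter rates are close to those of the largest trial in Table 11a (5.63% v 9.09%). These sizes assume lognormal volumes, scans missing at random and the stroke volumes implied by Tables 4 and 5.

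A reader might infer that the sensitivity analysis always leans toward the device and so looks more reassuring than it should. The documents do not support that. If the device raised stroke, the leak would reverse. Under the plan's own lesion-free rates, the linear model's treatment of zeros pulls the other way and, on the untransformed scale, by more. A reader might also take the NIHSS half as equally established. The same logic applies, but no lesion volumes by NIHSS worsening are given, so its contribution cannot be quantified. Nor do the documents support scaling the effect up to much heavier missingness: they assume 15% for Phase II and 20% for Phase I.

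**What to change.** In 12.4.3, add two covariates to the PROC MI model: stroke with onset before the DW-MRI, and NIHSS worsening at 2-5 days. Do not use 30-day death/stroke status. It mixes in strokes after the scan and non-neurological deaths, neither of which can explain a day 2-5 lesion volume.

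Both items are already collected, so the cost is a few lines of code and a sentence in the plan. There is a small downside: NIHSS will itself be missing in some subjects (5% loss is assumed for everything other than MRI), and the same imputation model must handle it. Fitting only in subjects free of both events would also work, but leaves fewer data behind a 17-covariate model. The handling of lesion-free zeros is a separate matter that these covariates do not settle.

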In addition, in the final analysis, assessments of study-center and of region effect on the primary safety endpoint will be carried out on the interventional group within the AT population using logistic regressions. A 0.15 level of significance will be used to assess the significance of each of the study center and region effects on the safety endpoint. A non-significant result for each of study centers and regions will support the pooling of patients across study centers and across regions for the primary safety analysis. A significant result will require further inspection of the by-center and by-region results to assess if poolability is appropriate. Note that centers with less than 5 subjects will be pooled with other centers by closest geographic region; this pooling will be carried out prior to the unblinding.

In addition, a logistic regression to assess the consistency of the primary safety endpoint rate across the following categories will also be performed on the interventional arm (separately for Phase I and Phase II) within the AT population:

- Subject gender (male versus female)
- Valve prosthesis type (Edwards vs. Medtronic)

- Operative risk (by Society of Thoracic Surgeons [STS] Risk Score)
- Type and duration of antiplatelet therapy:
 - Pre- and peri-procedural therapy:
 - Protocol-recommended antiplatelet therapy vs. other
 - Maintenance therapy:
 - Dual antiplatelet therapy (DAPT) to 90 days vs.
 - Monotherapy (aspirin or clopidogrel) to 90 days vs.
 - Warfarin with antiplatelet therapy to 90 days vs.
 - Other

As above, a 0.15 level of significance will be used to assess the significance of the difference of the primary safety endpoint rate across the subgroups of each factor.

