In the final analysis, assessment of treatment-by-study-center and treatment-by-region on the primary efficacy endpoint will be carried out on the eITT population using quantile regression. Total score obtained for each subject using the proposed approach (Finkelstein and Schoenfeld) will be the model dependent variable. The following two models will be built: 1.) Model inclusive of treatment, study center, and treatment-by-study center interaction, and 2.) Treatment region (US versus OUS, Phase I only), and treatment-by-region interaction. A 0.15 level of significance will be used to assess the significance of each of the study center and region effects on the efficacy endpoint. A non-significant result for each of study center and region will support the pooling of patients across study centers and across regions for the primary efficacy analysis. A significant result will require further inspection of the by-center and by-region results to assess if poolability is appropriate. Note that centers with less than 5 subjects will be pooled with other centers by closest geographic region; this pooling will be carried out prior to the unblinding.

Additionally, an assessment of treatment-by-study-center and treatment-by-region on each component of the primary efficacy endpoint will be carried out on the eITT population using analysis of variance on the cube root transformation for total lesion volume data and logistic regression for death/stroke and NIHSS worsening, with effects for 1.) Treatment, study center, and treatment-by-study center interaction, and 2.) Treatment, region (US versus OUS, Phase I only), and treatment-by-region interaction. As above, a 0.15 level of significance will be used to assess the significance of the interaction; a non-significant interaction or an interaction that is significant but only quantitative (and not qualitative) in nature will support the pooling of patients across study centers and across regions for the primary analysis; and centers with less than 5 subjects will be pooled with other centers by closest geographic region, with pooling carried out prior to the unblinding.

In addition, the above analysis will be repeated in the eITT population (separately in Phase I and Phase II analysis sets) to assess the consistency of treatment effects on each component of the primary efficacy endpoint across the following variables:

- Subject gender (male versus female)
- Valve prosthesis type (Edwards vs. Medtronic)

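### The poolability paragraph for the composite efficacy endpoint sets out to assess treatment-by-center and treatment-by-region interactions, but its decision rule names the center and region effects

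*Combined protocol and SAP*

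**What the plan says.** Section 12.4.3 contains two poolability paragraphs.

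**Composite score.** The aim is stated as "assessment of treatment-by-study-center and treatment-by-region on the primary efficacy endpoint will be carried out on the eITT population using quantile regression". The first model is described as "Model inclusive of treatment, study center, and treatment-by-study center interaction"; the region model also has an interaction term. The decision sentences follow: the 0.15 level is used to "assess the significance of each of the study center and region effects on the efficacy endpoint", then "A non-significant result for each of study center and region will support the pooling of patients across study centers and across regions". A significant result calls for a closer look at results by center and by region before pooling is judged. The region factor (US versus outside the US) is marked as applying to Phase I only.

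**Components.** For lesion volume, death/stroke and NIHSS worsening, "a 0.15 level of significance will be used to assess the significance of the interaction". Pooling is supported if the interaction is non-significant, or significant but only quantitative. This sentence opens by referring back to the paragraph above it. The consistency checks by sex, valve type, operative risk and antiplatelet therapy also use the interaction.

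**Safety, section 12.4.2.** The level is used to "assess the significance of each of the study center and region effects on the safety endpoint". That analysis is confined to the intervention arm.

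**The concern.** In the safety analysis there is only one arm, so a center or region effect is all that can be tested. In a comparison of two arms randomized within site, the terms answer different questions. A center effect says that sites differ in average outcome, which leaves the within-site device-control contrast intact. An interaction says that the contrast itself changes from site to site, which is what pooling concurrent subjects depends on. Section 5.2 has Phase II randomized 2:1, stratified by site.

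A rule that names the wrong term can err both ways. It can call for an unplanned judgment about the primary comparison when sites merely differ in case mix or imaging. It can also record support for pooling when the device effect changes direction between sites. The second matters more, because a non-significant result needs no further step.

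**Working it through.** The plan derives no figure here (0.15 is simply stated), so there is nothing to reproduce. The check has three steps.

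**1. Term by term**

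| | Stated aim | Model | Term given the 0.15 level |
|---|---|---|---|
| Composite (12.4.3) | treatment-by-center, treatment-by-region | includes interaction | center and region effects |
| Components (12.4.3) | same | includes interaction | interaction |
| Safety (12.4.2) | center, region | one arm, none possible | center and region effects |

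The composite row disagrees with its own first two cells. Its last cell matches the safety row.

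**2. What each term measures**

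For center *j* write: mean score = μ + τt + γ_j + δ_j·t, where γ_j is the center effect and δ_j the interaction. With t = ±½ and sum-to-zero centers (sum coding), γ_j is the center's shift in the *average of the two arm means*. With t = 0 for control and 1 for device (control-reference coding), γ_j is the center's shift *among controls*. The plan does not say which applies.

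- *Reversal with equal averages.* Center A: device +0.25, control −0.25. Center B: device −0.25, control +0.25. Both averages are 0, so the sum-coded center effect is zero. The device-control gaps are +0.5 and −0.5. Controls differ by 0.5, so the control-reference effect is not zero.
- *Reversal with equal controls.* Control 0 in both centers; device +0.5 and −0.5. The averages are +0.25 and −0.25, so the sum-coded effect reacts. The control-reference effect is zero.

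So under either coding some reversal is invisible to the center effect; which one depends on the unstated coding.

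**3. Rough size**

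Inputs from section 5.2: 225 subjects, 2:1, up to 25 sites (225/25 = 9 per site). A second layout used 15 sites of 15. Assumptions: a latent normal outcome with SD 1; between-site SD 0.3 or 0.5; device-control gaps of ±0.5 or ±1.0 alternating between sites. Scores were sums of win/loss signs over all pairs. Terms were tested by partial F test at 0.15, a least-squares stand-in for quantile regression. There were 2,000 runs per cell, so the Monte Carlo standard error is at most √(0.5×0.5/2000) = 0.011.

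Proportion with p < 0.15, 25 sites (15 sites in brackets):

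| Scenario | Center effect, sum-coded | Center effect, control-reference | Interaction |
|---|---|---|---|
| No heterogeneity | 0.15 (0.16) | 0.14 (0.15) | 0.14 (0.14) |
| Risk differs, SD 0.3 | 0.75 (0.81) | 0.40 (0.48) | 0.15 (0.16) |
| Risk differs, SD 0.5 | 0.99 (0.99) | 0.79 (0.84) | 0.15 (0.15) |
| Reversal, equal averages, gap ±0.5 | 0.14 (0.15) | 0.33 (0.41) | 0.63 (0.74) |
| Reversal, equal averages, gap ±1.0 | 0.15 (0.15) | 0.85 (0.91) | 1.00 (1.00) |
| Reversal, equal controls, ±0.5 | 0.67 (0.75) | 0.19 (0.17) | 0.66 (0.77) |
| Reversal, equal controls, ±1.0 | 1.00 (1.00) | 0.36 (0.30) | 1.00 (1.00) |

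The interaction test holds its level when only risk differs and reacts to both kinds of reversal. The center effect reacts to risk differences under either coding and is weak against one kind of reversal under each.

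**The case against.** The strongest reply is that the plan means the interaction. The opening sentence and the models say so, and the component rule refers back as if an interaction test had just been described. That stands in part. A reader might infer that the sponsor chose main effects in place of interactions; the text does not support this. It contradicts itself. A carry-over from the safety section is plausible but not documented.

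Several further points hold:

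- *Consequence.* One might infer that the rule rejects pooling or undoes the primary result. It does neither: a significant result prompts inspection. The 75–99% figures are rates of triggering that inspection.
- *Safeguard.* One might infer that a reversal would pass unseen. The component rule tests interactions and separates quantitative from qualitative ones. It does not name freedom from lesions, although that tier is volume zero and so is partly carried by lesion volume. What it leaves out is the composite score. No precedence is given if the two rules disagree.
- *Scenario.* The sum-coded center effect catches a reversal about as often as the interaction when controls are equal across sites (0.67 against 0.66).
- *Region.* The factor is limited to Phase I, and Phase II sites are all in the US, so for Phase II the issue is center.
- *Phase I controls.* It would be wrong to say that center or region risk never matters. The synopsis compares TriGUARD 3 subjects with controls from both phases, including 63 from Phase I if poolable. Phase I also enrolled in Europe and Israel, where there are no TriGUARD 3 subjects. For those non-concurrent controls, baseline risk differences can bias the comparison, and no treatment-by-center interaction for TriGUARD 3 can be estimated at such sites.
- *SAP.* Sections 5.1.1, 12.1 and 12.4.3 defer detail to a SAP. The text available here shows no separate rule that would settle this point.

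**Conclusion.** The point holds as an internal contradiction in a pre-specified rule. The aim and models concern interactions; the operative sentences for the composite name center and region effects. This rests on the text alone.

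The likely effect of following the sentences literally is frequent inspection caused by site risk alone (75–99% with sum coding and 40–84% with control-reference coding, against about 15%). A reversing effect would be flagged only at about the nominal level when site averages are equal and the term is sum-coded (14–15% against 63–100%). These figures show direction and rough size only. The site SDs and gaps are assumptions, since the documents give none; least squares replaces quantile regression; and the scores use all pairs, whereas 12.4.3 describes pairs across arms.

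Severity is minor to moderate. The primary test at one-sided 0.025 (section 12.2.1.1.2) is untouched. What is affected is whether its result can be read as common to all sites.

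**What to change.** In the first poolability paragraph of 12.4.3, replace the composite decision sentences with a rule to this effect:

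- the 0.15 level applies to the treatment-by-center interaction and, for Phase I, to the treatment-by-region interaction;
- an interaction that is non-significant or only quantitative supports pooling across centers (and, for Phase I, regions);
- a significant qualitative interaction leads to inspection of the results by center and by region.

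Keep center and region as main effects in the models. State the coding of the terms and the test used within the quantile regression.

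Leave the separate assessment of whether Phase I and Phase II controls can be pooled (synopsis, 5.1.1 and 12.4.3) unchanged, because differences in baseline site or region risk do matter there. The main-effect rule in 12.4.2 also stays.

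The cost is a few sentences of wording. The interactions are already in the models, so no new data, subjects or analyses are needed.
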